10.3. Adverse Events of Interest (AEOI)

10.3.1. Abnormal Liver Function Test Results

Abnormal liver function tests that meet the below criteria will be considered AEOIs and must be reported to the Sponsor's Medical Monitor within 24 hours of awareness if one of the following conditions are met:

- The abnormality represents a new elevation in ALT or AST >3 times the upper limit of normal (ULN), with or without an elevation of total serum bilirubin >2 times ULN; or
- The abnormality represents a 2-fold increase in ALT or AST above the baseline value for the double-blind period (ie, Day 1) in patients who had elevated values prior to starting study medication, or a 2-fold increase in ALT or AST above the baseline value for the open-label extension (ie, Week 112) in patients who had elevated values prior to starting open-label sparsentan.

In such instances, the following steps should be taken:

1. Temporarily discontinue study medication.
2. Perform repeat testing of ALT, AST, and total bilirubin, and test liver alkaline phosphatase isoenzyme within 48 to 72 hours to confirm the abnormalities.
3. If the abnormality is confirmed by repeat results:
 - a. Complete an AEOI Report Form that documents both the liver function test findings and any associated signs or symptoms and report by email to the SAE contact on the [Study Contact Information](#) page of this protocol.
 - b. Monitor liver enzymes and serum bilirubin 2 or 3 times weekly. The frequency of re-testing can decrease to once weekly or less if the abnormalities stabilize and the patient is asymptomatic.

- c. Perform additional testing to evaluate liver function, as appropriate (eg, international normalized ratio [INR], direct bilirubin).
4. Do not resume study medication until monitoring indicates abnormalities have resolved or stabilized.

Patients are not allowed to resume study medication if they have:

- ALT or AST >8 times ULN
- ALT or AST >5 times ULN for more than 2 weeks
- ALT or AST >3 times ULN and total bilirubin >2 times ULN or INR >1.5
- ALT or AST >3 times ULN with symptoms of fatigue, nausea, vomiting, right upper quadrant pain or tenderness, fever, rash and/or eosinophilia (>5% eosinophils)

Additionally, patients who demonstrate elevated liver enzymes a second time after re-introduction of the study medication may continue in the clinical trial; however, they will not receive study medication for the remainder of the trial.

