10.7. Reporting Adverse Events and Serious Adverse Events

10.7.1. Reporting Adverse Events

Adverse events (including SAEs) will be captured from the time informed consent is signed to the patient's final visit.

For patients who prematurely discontinue study treatment (see [Section 8.3.2](#)) but who are not withdrawn from the study, AEs will continue to be recorded until the patient completes the study (see [Section 6.3.1](#) for definition of patient completion).

If a patient initiates RRT after premature discontinuation of study treatment, only AEs and SAEs considered related or possibly related to study treatment need to be recorded.

Adverse events will be recorded using appropriate medical terminology. When recording, it is preferable to provide a diagnosis. In the absence of a diagnosis, each sign and symptom will be captured as a unique AE. Sufficient information should be sought to assist the Investigator both in determining the diagnosis and in making a causality assessment.

Reporting should not be delayed pending receipt of all required information. If information is unavailable at the time of the initial report, the Investigator is expected to follow-up until the required information has been obtained.

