10.7.2. Reporting Serious Adverse Events

The necessity and time requirements for reporting of SAEs to the Sponsor or its designee and/or regulatory agencies are as follows:

- All SAEs will be reported by email to the SAE contact on the [Study Contact Information](#) page of this protocol or by fax to the number in the Investigator Site File

- within 24 hours of the Investigator's first knowledge of the event, regardless of causal relationship.
- For the double-blind portion of the study (Day 1 through Week 112) and the open-label extension portion of the study (Week 112 and after), a completed SAE Report Form containing a detailed written description of the event along with available supporting documents (eg, discharge summary, autopsy report, diagnostic test results, etc.) will be provided by email to the SAE contact on the [Study Contact Information](#) page or by fax to the number in the Investigator Site File. For complete instructions, refer to SAE Report Form completion guidelines.
 - Additional information that is not available at the time the initial SAE Report Form was completed will be promptly reviewed and provided by email to the SAE contact on the Study Contact Information page or by fax to the number in the Investigator Site File within 48 hours of receipt. Full supporting documentation should be solicited by the investigative site even if the SAE occurred at another institution. Such documentation may include copies of relevant patient/hospital records, discharge summaries, laboratory/test results or autopsy reports.
 - If at any time after the patient has completed participation in the study (as defined in [Section 6.3.1](#) and [Section 6.3.2](#)), the Investigator or study staff becomes aware of an SAE that they suspect is related to the study medication (see [Section 10.6.1](#)), the event and any known details will be reported promptly by email to the SAE contact on the Study Contact Information page or by fax to the number in the Investigator Site File, following the reporting instructions in this section.

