10. SAFETY AND TOLERABILITY

Safety analyses will be conducted using the Safety Analysis Set at both interim and final analysis. At the interim analysis, all available data will be summarized. Unless otherwise noted, all safety analyses will be conducted using on-study data. All safety analyses specified below refer to the double-blind period only, except where noted. If >5% of patients initiate RRT while on study, select summaries excluding results after initiation of RRT may be prepared.

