10.1. Adverse Events

Adverse event (AE) data will be collected from the time that signed informed consent is obtained until the patient fully completes his/her participation in the study.

All AE summaries will be restricted to TEAEs, which is defined as any AE that newly appears, increases in frequency, or worsens in severity following the initiation of study medication. If it cannot be determined whether the AE is treatment emergent due to a partial onset date, then it will be counted as treatment emergent. Verbatim terms will be coded to PT and SOCs using MedDRA.

Each AE summary will be displayed by treatment group. Summaries that are displayed by SOC and PT will be ordered by descending order of incidence of SOC and PT within each SOC. Summaries of the following types will be presented:

- Overall summary of TEAEs
- Patient incidence of TEAEs and the total number of entries by SOC and PT
- Patient incidence of TEAEs and the total number of entries by PT in descending order
- Patient incidence of TEAEs by SOC, PT, and highest severity. At each level of patient summarization, a patient is classified according to the highest severity if the patient reported 1 or more events. AEs with missing severity will be considered severe for this summary.
- Patient incidence and total number of entries of severe TEAEs by SOC and PT. AEs with missing severity will be considered severe for this summary.
- Patient incidence of TEAEs by SOC, PT, and closest relationship to study medication (Related/Not Related). Related AEs are those with relationships reported as “Possibly Related” or “Related” and unrelated AEs are those with relationships reported as “Unlikely Related” or “Not Related.” At each level of patient summarization, a patient is classified according to the closest relationship to study medication if the patient reported 1 or more events. AEs with a missing relationship will be considered related for this summary.
- Patient incidence and total number of entries of related TEAEs by MedDRA SOC and PT. AEs with a missing relationship will be considered related for this summary.
- Patient incidence of serious TEAEs and the total number of entries by SOC and PT
- Patient incidence of TEAEs leading to treatment discontinuation by SOC and PT
- Patient incidence and total number entries of treatment-emergent adverse events of interest (AEOIs) by SOC and PT

- Patients incidence and total number of entries of TEAEs associated with safety topics of interest by PT

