10.1.1. Adverse Events of Interest

Abnormal liver function tests that meet the below criteria are considered AEOIs:

- The abnormality represents new elevation in alanine aminotransferase (ALT) or aspartate aminotransferase (AST) >3 times the upper limit of normal (ULN), with or without an elevation of total serum bilirubin >2 times ULN
- The abnormality represents a 2-fold increase in ALT or AST above the baseline value in patients who had elevated values prior to starting study medication.

As described in [Section 10.1](#), patient incidence of treatment-emergent AEOIs will be summarized by treatment group.

In order to explore the relationship between liver function abnormalities and study medication, the following time-to-event analysis will be performed:

- Time to first onset of treatment-emergent AEOI
 - The time to the start of the first occurrence will be calculated by the date of onset of first AEOI – date of first dose of study medication + 1
 - Patients who never reported an AEOI will be censored at the date of completion or discontinuation in randomized treatment period or data cut-off date of analysis, whichever is earlier
- Time to resolution of the most severe treatment-emergent AEOI
 - If multiple treatment-emergent AEOIs with the same preferred term with increasing severity were reported for the same patient, the time to resolution will be calculated by the date of resolution of the most severe event – start of the initial event + 1
 - Otherwise, the time to resolution will be calculated by the date of resolution of the event – start of the event + 1
 - Patients whose most severe treatment-emergent AEOI is ongoing will be censored at the date of completion or discontinuation in randomized treatment period or data cut-off date of analysis, whichever is earlier
 - Only patients who had reported a treatment-emergent AEOI are included in this analysis.

The analysis of time to event will include the number of patients with, the number of patients without event (censored), descriptive statistics of time for those with an event, and range in days for all patients. KM estimates will be calculated by treatment group. The quartiles, including the

median time-to-event and their respective 2-sided 95% CIs, will be presented. KM estimates will be plotted as a cumulative probability plot for each treatment group, with the number at risk identified.

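### SAP 10.1.1 counts liver AEOIs and their resolution through Week 112 but censors at the end of randomized treatment, which distorts two exploratory Kaplan-Meier curves

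*SAP*

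**What the plan says.** **Censoring.** For time to first onset, SAP 10.1.1 states: "Patients who never reported an AEOI will be censored at the date of completion or discontinuation in randomized treatment period". For time to resolution it states: "Patients whose most severe treatment-emergent AEOI is ongoing will be censored at the date of completion or discontinuation in randomized treatment period". In both, the data cut-off applies if earlier. Onset time is onset date minus first-dose date plus 1. Resolution time is resolution date minus start date plus 1. Neither is capped at the end of treatment.

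**Events.** SAP 10 sets the data scope: "Unless otherwise noted, all safety analyses will be conducted using on-study data", and "All safety analyses specified below refer to the double-blind period only, except where noted". Protocol 10.7.2 ends the double-blind portion at Week 112. SAP 10.1 defines a treatment-emergent event as "any AE that newly appears, increases in frequency, or worsens in severity following the initiation of study medication", which has a start bound and no end bound. For patients who stop drug early but stay in the study, protocol 10.7.1 says "AEs will continue to be recorded until the patient completes the study". Protocol Table 5 schedules chemistry, including ALT and AST, at both Week 108 and Week 112.

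**Drug handling.** The first step in protocol 10.3.1 when an AEOI is found is "Temporarily discontinue study medication". The section also lists findings after which drug may not be resumed, and asks for repeated enzyme checks each week once the abnormality is confirmed.

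The on-treatment limit in SAP 10.1.3 is written for selected TEAE summaries. It is not applied to these two curves.

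**The concern.** Kaplan-Meier estimation needs events and censoring to be observed over the same follow-up. Here late onsets and late resolutions count, while patients without them are removed at an earlier date.

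In the resolution analysis the censoring is also informative. An AEOI interrupts drug, and the more serious findings bar restart. Patients whose injury does not resolve and who never restart are therefore taken out of the risk set near drug stop, although their follow-up continues.

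In the onset analysis an event-free patient leaves at drug stop, but a patient with a later event stays at risk until that event. The denominators for late events are too small.

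At stake is how two liver-safety figures by arm would be read. SAP 10.1.1 introduces them as a way of exploring the relation between liver abnormalities and study medication.

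**Working it through.** **1. Day numbers.** With first dose as Day 1, the target day is 7 x week + 1. Week 108 gives 7 x 108 + 1 = 757 and Week 112 gives 7 x 112 + 1 = 785, both as in SAP Table 2. With the protocol visit windows, Week 108 falls on Days 750 to 764 (±7) and Week 112 on Days 778 to 799 (-7 to +14).

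**2. Which date is the censoring date?** SAP 4.1 describes a 108-week blinded treatment period. SAP 8.7.2 calls Week 112 the point four weeks after cessation of randomized treatment. SAP 10.1.3 adds the time up to the first open-label dose for those who completed the randomized treatment period. All three put the end of that period before Week 112.

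**3. Resolution: censoring time of an ongoing AEOI.** The SAP rule gives end of treatment - onset + 1. Follow-up to Day 785 gives 785 - onset + 1. The onset and stop days are examples.

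| Onset | End of treatment | SAP rule | Followed to Day 785 |
|---|---|---|---|
| 785 | 757 | -27 | 1 |
| 500 | 200 | -299 | 286 |
| 300 | 300 to 305 (permanent stop) | 1 to 6 | 486 |
| 300 | 757 (resumed and completed) | 458 | 486 |

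**4. Resolution: effect on the curve.** Assume 10 AEOI patients who all stop drug within 4 days of onset. Six resolve on days 14, 21, 28, 42, 56 and 70, and four do not resolve. The median is taken as the first time at which half have resolved.
- SAP rule: the four unresolved patients leave by day 4, so 6 are at risk. The curve is 1/6, 2/6, 3/6 at day 28, and 6/6 at day 70. Median 28 days, 100% resolved.
- Censoring at last contact after day 70: 10 are at risk. The curve is 5/10 at day 56 and 6/10 at day 70. Median 56 days, 60% resolved.

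If the six resolve on days 14, 21, 28, 28, 35 and 42, the medians are 28 and 35 days. The size of the shift depends on the days assumed; its direction does not.

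**5. Onset before Week 112.** Assume an AEOI hazard of 2.5% per year. True incidence at Day 757 is 1 - exp(-0.025 x 757/365.25) = 5.05%. Early drug stop is simulated as uniform over Days 15 to 757.
- Everyone followed to Day 785, same hazard off drug: about 5.6%, 6.0% and 6.4% for 20%, 30% and 40% early stop.
- Half of the early stoppers followed: about 5.3%, 5.5% and 5.8%.
- Half followed and the off-drug hazard halved: about 5.3%.

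**6. Onset at Week 112.** On-schedule event-free patients are censored by Day 764, so a first AEOI on Day 785 has a risk set of 1 and contributes the factor 1 - 1/1 = 0. Assume 150 per arm, one AEOI on Day 785, and 10% to 40% early stop. Under last-contact censoring, half of the early stoppers are followed to Week 112.

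| Earlier AEOIs | SAP rule, before → after Day 785 | Censored at last double-blind contact | Crude |
|---|---|---|---|
| 0 | 0% → 100% | 1.1–1.2% | 1/150 = 0.7% |
| 3 | 2.1–2.6% → 100% | 3.1–3.5% | 4/150 = 2.7% |
| 8 | 5.7–7.1% → 100% | 6.4–7.2% | 9/150 = 6.0% |

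With last-contact censoring, 80 to 102 patients are at risk on Day 785. Under the SAP rule all three quartiles become Day 785. At 2.5% per year with full follow-up, the expected number of first AEOIs between Days 757 and 785 in 150 patients is 150 x [exp(-0.0518) - exp(-0.0537)] ≈ 0.27. The chance of at least one is then 1 - exp(-0.27) ≈ 24%.

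**The case against.** **The censoring date is not defined.** SAP 10.1.1 does not say treatment completion or last dose, although SAP 8.8.2.3 and 10.1.3 are explicit elsewhere, and SAP 7.1 separates stopping drug from leaving the double-blind period. If the sponsor meant completion of, or withdrawal from, the whole double-blind period, the mismatch disappears. This stands as a limit on certainty. The usage in step 2 makes end of treatment the likelier reading, and the sentence needs rewording either way.

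**The censoring phrase could itself limit the analysis to the treatment period**, so that Week 112 onsets do not count. SAP 10.1.1 states no such limit on events.

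**Censoring near onset is not universal.** Protocol 10.3.1 first interrupts drug temporarily, and one bar on restart (ALT or AST above 5 times ULN for more than 2 weeks) cannot be known at once. A patient who resumes and completes loses only about four weeks. The point concerns permanent stops, and how near onset the censoring falls depends on how discontinuation is dated.

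**The magnitudes rest on assumed inputs.** Neither document gives an AEOI rate, a stop rate or resolution times. Continued visits after early stop are only encouraged (protocol 6.4.2).

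**A reader might infer that these are the SAP's only liver analyses, or that severe injury would be hidden.** The SAP does not support that. AEOI incidence (10.1), Hepatic Disorders SMQ summaries both on study and on treatment (10.1.2), CTCAE shifts (10.4.2), and liver-test categories with a listing of combined bilirubin and transaminase elevations (10.4.3) do not use this censoring rule.

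**Conclusion.** The rule is wrong as most naturally read, at minor to moderate severity.

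The firmest part is resolution. Unresolved AEOIs with permanent drug stop are censored early while late resolutions count, so recovery is overstated. Ongoing AEOIs that start after drug stop get impossible times. The mechanism follows from the text; the size depends on assumed cases.

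For onset, the upward bias before Week 112 runs from a few tenths of a point to about one point under the assumed rates.

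A reader might infer that the onset curve will end at 100%. That happens only at the final analysis, and only if a first AEOI falls after the last event-free patient in that arm has been censored. A late Week 108 visit could leave others at risk. At the interim, many patients should still be on drug. The plot must show numbers at risk, so a risk set of one would be visible, but the quartiles would still be uninterpretable.

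A reader might also infer a bias favouring one arm. The documents give no discontinuation or AEOI rates by arm, so a difference is possible but cannot be asserted.

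The curves are exploratory, with no between-arm test specified. Crude incidence and the efficacy type I error are not touched.

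**What to change.** Change two sentences in SAP 10.1.1.

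- **Onset.** Use the same end date for events and censoring. Either count AEOIs to last double-blind contact and censor event-free patients there, or apply the SAP 10.1.3 on-treatment window to both. That window has no stated end for completers who do not enter the open-label extension, so last double-blind contact would have to serve for them. Data cut-off applies if earlier.
- **Resolution.** Censor ongoing AEOIs at the last double-blind AE or laboratory assessment or data cut-off, whichever is earlier.

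If the whole double-blind period was meant all along, the rewording should say so. A programming check that all times are at least 1 day would catch what remains. The cost is two sentences and no new data, because AE follow-up and Week 112 chemistry are already collected.

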10.1.2. Other Safety Topics of Interest

The following summaries of TEAEs associated with safety topics of interest will include incidence of TEAE, treatment related TEAE, and serious TEAEs by PT and will be prepared separately for TEAEs on-study and on-treatment. All Sponsor-defined terms will be identified prior to database lock for the interim analysis and will be included in the clinical study report.

- Cardiovascular System associated TEAEs comprised of terms in the Cardiac SOC, Vascular SOC, and Cardiac Arrhythmias Standardized MedDRA query (SMQ). Separate summaries of terms in the Cardiac Arrhythmias SMQ will also be prepared.
- Hypotension associated TEAEs comprised of Sponsor-defined terms
- Hepatic associated TEAEs comprised of terms in the Hepatic Disorders SMQ, excluding the following sub-SMQs: alcohol related sub-SMQ, congenital, familial, neonatal and genetic disorders of the liver; liver infections; and pregnancy-related hepatic disorders
- Pancreatic associated TEAEs comprised of terms in the Acute Pancreatitis SMQ
- Fluid Retention associated TEAEs comprised of terms in the Haemodynamic Oedema, Effusions, and Fluid Overload SMQ
- Anemia associated TEAEs comprised of Sponsor-defined terms

10.1.3. On-Treatment Summaries

Select summaries for TEAEs while on-treatment will additionally be prepared. On-treatment will be defined as TEAEs starting ≤ 30 days from date of last dose in randomized treatment period for patients who discontinue treatment or any TEAE prior to first dose in OLE for patients who complete the randomized treatment period. Summaries will be prepared for TEAEs associated with safety topics of interest in Section 10.1.2. Patient incidence of on-treatment TEAEs and the total number of entries by PT will also be provided.

10.1.4. Adverse Events during OLE

At the interim analysis, summaries of adverse events with onset on or after the first dose of sparsentan in the OLE will be presented for the OLEFAS by randomized treatment group and overall. Time-to-event analyses will not be performed due to the anticipated small sample size.

10.2. Extent of Exposure and Compliance

The following extent of exposure parameters will be summarized both continuously using descriptive statistics and categorically using counts and percentages by treatment group and overall:

- Duration of treatment (weeks)
- Duration of treatment with initial/reduced dose (weeks)

- Duration of treatment with target dose (weeks)
- Time to titration to target dose (weeks)
- Total duration of study medication interruptions (days)

Duration of treatment (weeks) will be calculated as follows:

- Duration of treatment = (Date of last dose of study medication – Date of first dose of study medication + 1) / 7

Duration of treatment with initial/reduced dose and duration of treatment with target dose will be calculated similarly. For patients who received the target dose on Day 1, the duration of treatment with initial/reduced dose will be set to 0.

For patients who titrated to the target dose, the time to titration to target dose (weeks) will be calculated as follows:

- Time to titration to target dose = (Date of first dose of target dose – Date of first dose of study medication + 1) / 7

The duration of each incidence of study medication interruption will be calculated as follows:

- Duration of study medication interruption = (Date of restart of study medication – Date of temporary discontinuation)

The total duration of study medication interruptions is the sum of duration of study medication interruption over each incidence of interruption. For patients with no study medication interruption, the total duration is considered 0 days.

A summary of patients who had dose modifications will be presented by frequency count and percentages:

- Titration to target dose
- Dose reductions after titration to target dose

Patient's compliance rate (%) with study medication during the treatment period will be calculated as follows at the final analysis:

- $100 \times \{(\text{Total number of capsules dispensed} - \text{Total number of capsules returned}) / (\text{Expected number of capsules to be taken based on the patient's titration schedule})\}$

Compliance rates will be summarized both continuously using descriptive statistics and categorically using counts and percentages by treatment group and overall.

Compliance will also be derived from the dose log to supplement the assessment using drug dispensation and return. Compliance based on the dose log for each patient will be determined as follows:

- Total number of capsules taken = sum over all actual dose intervals, where an actual dose interval is defined as any dose log record where actual dose > 0 capsules and derived as number of days × number of capsules

- Total number of capsules missed = sum over all missed dose intervals defined as any record where dose = 0 capsules and eCRF indicates missed dose; derived as number of days × number of expected capsules
- Total number of capsules taken over prescribed dose = sum of all dose intervals where dose log indicates overdose and derived as number of days × number of capsules
- Dose log compliance = $100 \times (\text{Total number of capsules taken}) / (\text{Total number of capsules taken} + \text{Total number of capsules missed} - \text{Total number of capsules taken over prescribed dose})$

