8.3.2. Dose Modification, Reduction, or Discontinuation

Patients who display asymptomatic blood pressure values $\leq 100/60$ mmHg (patients ≥ 18 years of age) or $\leq 90/50$ mmHg or are below the 5th percentile for sex and height (whichever is lower in patients < 18 years of age), or who present with clinical symptoms of orthostatic hypotension (see [Section 9.6](#)) but otherwise tolerate the initial dose will continue after the Week 2 visit (or the Week 114 visit for the open-label extension) without titrating up to the target dose. Patients who do not titrate up to the target dose at Week 2 (or Week 114) may titrate up to that dose at any time, based on evaluation of the Investigator, in consultation with the Medical Monitor as needed. Reductions from the target dose back to the initial dose are permitted at any time after titrating up to the target dose.

Patients weighing > 50 kg at screening who do not tolerate the initial dose for any reason may continue at one-half the initial dose at the Investigator's discretion and in consultation with the Medical Monitor, as needed. Patients weighing ≤ 50 kg at screening who do not tolerate the initial dose for any reason will be discontinued from the study.

In patients with temporary dose interruptions, treatment should be resumed whenever possible (including between visits), and treatment resumption should be considered at every visit following study medication interruption.

Doses may be modified at any time throughout the open-label extension for safety/tolerability reasons at the Investigator's discretion. In addition, after titration to the target dose for the open-label extension, increases above the target doses of 200 mg or 400 mg sparsentan may be considered for patients who, in the Investigator's opinion (and following consultation with the Medical Monitor), would benefit from an increased dose.

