4.2. Definition of Study Drugs

4.2.1. Double-Blind Period

Sparsentan will be dispensed as 200-mg tablets overencapsulated (blinded) with size 00 capsules, and irbesartan (active control) will be dispensed as 75-mg tablets overencapsulated (blinded) with size 00 capsules.

For patients with screening body weight >50 kg, the initial starting dose for study drug is 2 capsules (sparsentan 400 mg or irbesartan 150 mg), whereas for patients with screening body weight ≤50 kg, the initial starting dose is 1 capsule (sparsentan 200 mg or irbesartan 75 mg). Weight will be measured at each study visit, and the dose may be increased at the Investigator's discretion if the patient's weight reaches >50 kg.

At the Week 2 visit, the Investigator will evaluate dose tolerance in a blinded manner prior to titrating up to the target dose of 4 capsules (sparsentan 800 mg or irbesartan 300 mg) for patients with screening weight >50 kg, or 2 capsules for patients with screening weight ≤50 kg. Patients may continue on the initial dose without titration or have dose reductions back to the initial (reduced) dose after dose titration based on tolerability as described in the [protocol](#). At the Investigator's discretion, patients with screening weight >50 kg who do not tolerate the initial dose for any reason may continue at one-half the initial dose, 1 capsule (sparsentan 200 mg or irbesartan 75 mg).

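### Read literally, SAP 10.2 double-counts weeks when a patient returns to an earlier dose level, and it gives the one-half initial dose no duration line

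*SAP*

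**What the plan says.** SAP 10.2 gives one duration formula: "Duration of treatment = (Date of last dose of study medication – Date of first dose of study medication + 1) / 7". For the two dose levels it reports, it adds only: "Duration of treatment with initial/reduced dose and duration of treatment with target dose will be calculated similarly". The single special case is: "For patients who received the target dose on Day 1, the duration of treatment with initial/reduced dose will be set to 0".

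The same section sums where it wants a sum. On interruptions: "The total duration of study medication interruptions is the sum of duration of study medication interruption over each incidence of interruption". On dose-log compliance: "Total number of capsules taken = sum over all actual dose intervals".

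Dose may go down. Protocol 8.3.2 states: "Reductions from the target dose back to the initial dose are permitted at any time after titrating up to the target dose". SAP 4.2.1 says the same: patients may "have dose reductions back to the initial (reduced) dose after dose titration based on tolerability". Protocol Table 2 puts initial and reduced dose in one column and the one-half initial (double reduced) dose in another, the latter available only above 50 kg. SAP 4.2.1 also describes this third level. The exposure parameters in SAP 10.2 list durations for initial/reduced and target only, and the dose-modification summary has two rows: titration to target, and reduction after titration.

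**The concern.** A first-to-last formula measures time at a dose level only if that level is taken in one unbroken block. Here the initial/reduced category is entered at the start of treatment and can be entered again after a step-down, with the target period in between. Target dose can likewise be taken in two blocks with a reduced period between them. In either case the span from first to last date at one level takes in weeks spent at the other.

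These are the only summary parameters in SAP 10.2 for how long each arm spent at target dose. A reader of the study report will use them to judge how far the results reflect that dose. The error arises only in patients whose dose changes, so arms with different patterns of change would be distorted to different degrees. Patients moved to the one-half initial dose are among the least tolerant, and their time at that dose has no line of its own.

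**Working it through.** **Inputs.** The formula and the set-to-zero rule are from SAP 10.2. The dose levels are from protocol Table 2. Treatment lasts 108 weeks, or 756 days (SAP 4.1). The days of dose change are illustrative assumptions; the documents give none.

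**Two calculations per level.** Literal rule: (last day at level − first day at level + 1)/7. True time: sum over all intervals at the level of (stop − start + 1), divided by 7.

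**The rule works for up-titration only.** Initial Days 1–14, target Days 15–756: 14/7 = 2.0 and 742/7 = 106.0, total 108.0.

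**It fails on return to a level.**

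- *A. Initial 1–14, target 15–350, reduced 351–756.* Initial/reduced by rule: 756/7 = 108.0; true: (14 + 406)/7 = 60.0. Target: 336/7 = 48.0, correct. Reported total 156.0, an excess of 48.0.
- *B. Initial 1–14, target 15–100, reduced 101–600, target 601–756.* Target by rule: 742/7 = 106.0; true: (86 + 156)/7 = 34.6. Initial/reduced by rule: 600/7 = 85.7; true: (14 + 500)/7 = 73.4. Reported total 191.7.
- *C. Initial 1–14, target 15–210, reduced 211–280, target 281–756 (a 10-week reduction).* Initial/reduced by rule: 280/7 = 40.0; true: (14 + 70)/7 = 12.0. Target by rule: 742/7 = 106.0; true: (196 + 476)/7 = 96.0. Reported total 146.0, an excess of 38.0.

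In the pattern of A, all target time is counted twice. A step-down after week 10 adds (70 − 15 + 1)/7 = 8 weeks; one after week 100 adds (700 − 15 + 1)/7 = 98.

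**Moves to one-half initial dose are a different error.**

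- *D. Initial 1–14, one-half initial 15–756.* Reported: 2.0 + 0. The other 742/7 = 106.0 weeks fall under no dose level, and the patient is in neither dose-modification row.
- *E. Initial 1–14, target 15–350, one-half initial 351–756.* Reported: 2.0 + 48.0 = 50.0; 406/7 = 58.0 weeks fall under no level.
- *F. Initial 1–14, one-half initial 15–140, initial 141–756.* Initial/reduced by rule: 108.0; true: (14 + 616)/7 = 90.0. Here the 126/7 = 18.0 weeks at one-half initial are absorbed into initial/reduced.

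**The set-to-zero rule.** Target 1–350, reduced 351–756: initial/reduced is set to 0 although 406/7 = 58.0 weeks were taken.

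**With summing.** Histories A to F each total 108.0 weeks across the three levels.

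**The case against.** The strongest reply is that the SAP never writes a per-level formula. A programmer would notice dose-level times exceeding total treatment time and would sum instead, so the gap is one of wording. That is partly right: the first-to-last reading is an inference, though the literal one. It is hard to call summing implied when the same section spells it out for interruptions and for dose-log capsules but not here.

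The dose histories are invented, and A and B have long reduced periods (406 and 500 days). That stands, but C shows that a 10-week reduction still produces 38 excess weeks.

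Three stronger readings might tempt a reader, and the documents do not support them.

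- *Every dose reduction is double-counted.* Moves from initial or target to one-half initial that are not followed by a return leave time unreported. The rare patient at target on Day 1 who is later reduced and stays there is under-counted. Protocol 8.1.1 starts everyone on the initial dose for two weeks, so that group should be almost empty.
- *The third level goes wholly unreported.* It enters overall duration and dose-log compliance, SAP 6.1 plans by-patient listings, and a drop from target to one-half initial would count as a reduction after titration.
- *Tolerability cannot be compared between arms.* SAP 10.1 and 10.2 also plan counts titrated and counts reduced, time to titration, interruption time and adverse events leading to discontinuation. None of these uses the disputed durations.

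**Conclusion.** The point holds in a limited form. As written, the rule gives wrong dose-level durations for patients who return to a level, and time at the one-half initial dose has no line of its own. For a single patient the error can be large: 48 excess weeks in A, and 106.0 target weeks reported against 34.6 true in B.

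The size by arm is unknown, because the documents give no expected rate or timing of reductions. A reader might infer that the arms will be distorted unequally; that depends on unequal dose changes, which nothing in the documents establishes. The conclusion rests on the literal reading of SAP 10.2. If the sponsor already intends to sum intervals, the double count disappears and the missing third level remains. Protocol 12.6 asks only for overall duration, which is unaffected. No efficacy estimate, test or power figure is touched. This is a correction to descriptive exposure tables that is worth making.

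**What to change.** In SAP 10.2:

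1. Define time at each dose level as the sum of days over all dose-log intervals at that level, divided by 7.
2. Give the one-half initial level its own duration line and add moves to it to the dose-modification summary. Assign levels from capsules and the Table 2 weight row, because one capsule is the one-half initial dose above 50 kg but the initial dose at or below it.
3. Delete the set-to-zero rule, since summing gives zero whenever zero is true.
4. Footnote that dose-level times plus off-drug days equal the first-to-last treatment duration. Overall duration includes interruptions, which are reported separately, so without the note the levels would seem not to add up.

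The cost is a few lines of SAP text and a small programming change. The dose log already holds the intervals, since dose-log compliance uses them, so no new data are needed and no dosing rule changes. If the SAP is not amended, the change can be recorded as a deviation in the clinical study report, as SAP Section 2 provides.
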